9.4.1 Efficacy Endpoints

The primary efficacy endpoint is OR. For Cohorts A-F, response for the primary analysis will be determined by investigator assessments in initial cohorts and by BICR in cohorts that expand (combining the initial and expansion cohorts), with confirmatory assessment as required per RECIST 1.1 and RANO. For Cohort G, response for the primary analysis will be determined by BICR, with confirmatory assessment as required per RECIST 1.1. The ORR, defined as the proportion of participants who have a best overall response of either CR or PR using RECIST 1.1 (or RANO for GBM participants) at any time during the study, will be analyzed. Participants with unknown or missing response information will be treated as nonresponders.

Secondary Efficacy Endpoints

1. Disease control, defined as the best overall response of CR, PR, or stable disease based on RECIST 1.1.
2. DOR, defined in the subset of participants with a CR or PR, based on RECIST 1.1 (or RANO for GBM participants), as the time from first documented evidence of CR or PR until the first documented sign of disease progression or death due to any cause, whichever occurs first.
3. PFS, defined as the time from date of study treatment to the first documented disease progression based on RECIST 1.1, modified to follow a maximum of 10 target lesions and a maximum of 5 target lesions per organ (or RANO for GBM participants) or death due to any cause, whichever occurs first.
4. OS, defined as the time from the date of study treatment to the date of death due to any cause.

OR, DCR, DOR, and PFS based on iRECIST by investigator assessment are exploratory endpoints in participants who received pembrolizumab + lenvatinib combination therapy. The details on these exploratory endpoints will be provided in the supplemental SAP.

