Steroid dose is defined as the average daily dose since last visit. A dose of "none" means no corticosteroids above physiologic replacement dose. The dose is considered "stable" if it is unchanged or decreased from the visit at which the scans showed the smallest tumor burden. The dose is considered "increased" if it has increased from the visit at which the scans showed the smallest tumor burden.

For any overall response except PD, all the components of the definition (radiological, neurological, and steroid dose) must be present ([Table 19](#)). However, either radiological progression or clinical deterioration (not attributable to a nontumor-related cause) qualifies a participant for PD. However, an increase in steroid dose alone is not sufficient for an overall visit response of PD in the absence of clinical or radiological evidence of progression. A participant with a radiological response of stable disease, and without neurological evidence of progression, but requiring an increased dose of steroids, would still be considered stable disease overall at that visit (because increase in steroids alone is not PD). However, the participant will be reassessed at the next visit. If either radiological or neurological progression is documented at that next visit, the visit at which the increased dose was first observed would be retroactively reassessed as PD overall.

Table 19 Overall Response

Radiographic Response	Clinical Performance	Steroid Dose	Overall Response
CR	Stable	None	CR
CR	Stable	Stable or increased	PR
PR	Stable	Stable	PR
PR	Stable	Increased	SD
SD	Stable	Stable	SD
SD	Stable	Increased	SD or PD ^a
PD	Any	Any	PD
Any	Worsening	Any	PD
NE	Stable	Increased	NE or PD ^a
NED	Stable	Increased	NED or PD ^a

CR = complete response; NA = no lesions of this type were present at baseline; NED = no evidence of disease (no enhancing lesions were present at baseline, and no new lesions have appeared); PD = progressive disease; PR = partial response; SD = stable disease.

^a PD should not be based on an increase in steroid dose alone, unless confirmed by radiographic or clinical deterioration. If the steroid dose is increased while the radiographic assessment and clinical performance are stable, the participant should be re-evaluated at the next visit. If clinical or radiographic deterioration has occurred, progression can be retrospectively assigned at the visit when the steroid dose was increased.

Pseudoresponse and response confirmation

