Pseudoresponse is a phenomenon observed in patients treated with antiangiogenic therapy, and manifests as a transient decrease in tumor enhancement that does not reflect a true reduction in tumor burden. To avoid mistaken reporting of pseudoresponse as OR, a visit response of PR or CR must be confirmed with a scan performed at least 4 weeks later that shows the same category of response or better. That is, a PR can be confirmed with a subsequent PR or CR, and a CR must be confirmed with a subsequent CR.

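### RANO Table 19 lets a radiographic CR on an increased steroid dose count as an objective response in Cohort E, while a radiographic PR on an increased dose does not

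*Combined protocol and SAP*

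**What the plan says.** Section 9.4.1 takes as the primary efficacy measure "The ORR, defined as the proportion of participants who have a best overall response of either CR or PR", with RANO replacing RECIST 1.1 for glioblastoma and confirmation required.

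Appendix 10 (Section 10.10) describes how each visit is scored. The radiographic response from Table 18 is combined with clinical status and corticosteroid dose in Table 19. The introductory text reads "For any overall response except PD, all the components of the definition (radiological, neurological, and steroid dose) must be present".

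Two rows of Table 19 matter here (columns: radiographic response, clinical performance, steroid dose, overall response):

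- "CR Stable Stable or increased PR"
- "PR Stable Increased SD"

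The steroid reference is the visit with the smallest tumor burden on scan, not baseline. A dose at or below the dose at that visit is stable, and a higher one is increased.

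On confirmation, a later scan at least 4 weeks on must show the same category or better, so "a PR can be confirmed with a subsequent PR or CR". That rule sets no separate steroid condition.

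Steroid use is possible in this cohort. Section 5.2.1 allows a limited stable dose at entry, and Section 6.5.2 allows on-study corticosteroids after consultation with the sponsor.

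**The concern.** The steroid component exists so that a scan change is read together with the dose the participant was taking. For a radiographic PR it does that work: a stable dose gives a responder and an increased dose a nonresponder. For a radiographic CR the two dose categories are merged into "Stable or increased", so an increase has no consequence beyond that of a stable dose, and the visit is still a response.

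At stake is who counts as a responder in the primary endpoint of a single-arm cohort. Cohort E has no comparator to absorb misclassification, and the reported result is the ORR with its exact confidence interval (Sections 9.1 and 9.3).

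**Working it through.** The plan has no figure of its own to reproduce on this point. The interval tables in Section 9.9 are redacted, and no sample size depends on the row. The check is a reading of the table, followed by an illustration of size.

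**Step 1: map the relevant rows to responder status.** Clinical status is stable throughout. A responder is an overall CR or PR (Section 9.4.1).

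| Radiographic | Steroid dose | Overall (Table 19) | Counts in ORR |
|---|---|---|---|
| CR | None | CR | Yes |
| CR | Stable | PR | Yes |
| CR | Increased | PR | Yes |
| PR | Stable | PR | Yes |
| PR | Increased | SD | No |
| SD | Stable | SD | No |
| SD | Increased | SD or PD | No |

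For a radiographic CR, no level of the steroid component changes responder status. For a radiographic PR, an increase does.

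**Step 2: follow the rows through confirmation, under both readings of the steroid reference visit.** The appendix does not say whether the smallest-burden visit can be the visit being scored.

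- *Reference can be the current visit.* At a first radiographic CR all enhancing lesions have gone, so that visit is itself the smallest-burden visit and its dose is compared with itself. It cannot be increased, even if it rose after baseline. The same holds for a first PR at a new minimum. The merged row then matters at later visits. Suppose a first CR is scored PR on steroids, and a second CR at least 4 weeks later is on a higher dose, with the first CR visit taken as the reference. The second visit scores PR, and PR followed by PR is confirmed. The parallel case with two radiographic PRs, the second no smaller and on a higher dose, gives PR then SD and is not confirmed by that visit.
- *Reference is an earlier visit only.* A first radiographic CR on a raised dose can now fall in the merged row and score PR. It can confirm an earlier PR, and two such visits at least 4 weeks apart give PR followed by PR, a confirmed response. A radiographic PR on the same raised dose would score SD each time.

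The difference in treatment between CR and PR is present on both readings. What changes is where it has effect: mainly confirmatory visits on the first reading, qualifying visits as well on the second.

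**Step 3: size.** One participant reclassified from responder to nonresponder changes ORR by 1/100 = 1.0 point, or 1/30 = 3.3 points. This applies only if that participant has no other qualifying confirmed response. The exact (Clopper-Pearson) 95% limits for x responders of n are the 2.5% quantile of Beta(x, n−x+1) and the 97.5% quantile of Beta(x+1, n−x). The starting responder counts and the numbers removed are assumptions:

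| n | Removed | Responders | ORR | Exact 95% CI |
|---|---|---|---|---|
| 100 | 0 | 15 | 15.0% | 8.6 to 23.5 |
| 100 | 1 | 14 | 14.0% | 7.9 to 22.4 |
| 100 | 2 | 13 | 13.0% | 7.1 to 21.2 |
| 30 | 0 | 5 | 16.7% | 5.6 to 34.7 |
| 30 | 1 | 4 | 13.3% | 3.8 to 30.7 |
| 30 | 2 | 3 | 10.0% | 2.1 to 26.5 |

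The number affected could be zero.

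**The case against.** The strongest defence is that the table works as a one-category downgrade: an increased dose takes CR to PR and PR to SD. A CR on any dose above replacement is already denied CR, so the steroid component is not ignored. A sponsor could also hold that a radiographic PR on rising steroids may be regrowth above the minimum, which deserves stricter treatment than sustained absence of enhancement. This may be what was intended. It does not explain why, in the CR row alone, an increase costs nothing beyond a stable dose, and no rationale is stated.

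The reference-visit argument largely stands. If the current visit can be the reference, a first CR is scored on a stable or nil dose, the merged row is reached only later, and splitting it leaves first responses on a raised dose untouched. This limits the effect but does not remove the asymmetry.

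The row is also narrow. It needs disappearance of all enhancing lesions, no T2/FLAIR increase, no new lesions and stable clinical status. The imaging charter and the redacted efficacy-methods section may say more.

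A reader might infer three stronger things that the documents do not support:

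- *That the sentence on components contradicts the table outright.* It may mean only that each component must be available, and the same paragraph keeps a radiographic SD on an increased dose as SD. It is supporting evidence; the two rows carry the point.
- *That the steroid component is the safeguard against antiangiogenic pseudoresponse.* Appendix 10 handles pseudoresponse through the confirmatory scan.
- *That the decision to expand Cohort E hangs on this row.* Section 4.1.1 already states that Cohort E will be expanded.

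**Conclusion.** The point holds as an inconsistency between rows of Table 19. An increased steroid dose turns a radiographic PR into a nonresponse but leaves a radiographic CR as a response, and such a CR visit can qualify for or confirm objective response in Cohort E's primary ORR. The conclusion rests on the table and the ORR definition as printed, and it survives either reading of the steroid reference visit.

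The effect is probably small: 1.0 point at N=100 or 3.3 points at N=30 per affected participant without another qualifying confirmed response. The frequency is not given, and the 0 to 2 participants shown are an assumption. No sample size changes, and there is no hypothesis test to affect. The point is worth correcting because it concerns a primary-endpoint rule and costs little, not because a large bias has been shown.

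**What to change.** Split the second row of Table 19 into two:

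- CR / Stable / Stable = PR
- CR / Stable / Increased = SD

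This matches the treatment of a radiographic PR.

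In the steroid-dose paragraph, state whether the smallest-tumor-burden reference visit can be the visit being scored. Without that, the reach of the split is undefined: if it can, a first CR or PR on a raised dose is scored as stable and the split acts mainly on confirmatory visits.

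If the sponsor prefers to keep the merged row, the appendix should say why CR and PR differ, and ORR should also be reported with CR visits on an increased dose treated as nonresponse.

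The cost is one table row, one sentence and the matching line of the imaging charter. No new data are needed, and no image has to be re-read because the radiographic response is unchanged. As this is a primary-endpoint rule, Section 9 routes the change through a protocol amendment. The downside is that a true CR in a participant whose steroids were raised for another reason is credited only at a later scan, once the dose is stable or nil, as already happens for a radiographic PR.

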10.11 Appendix 11: Abbreviations

Abbreviation	Expanded Term
1L	first-line
2L	second-line
ACRIN	American College of Radiology Imaging Network
ADL	activities of daily living
AE	adverse event
AJCC	American Joint Committee on Cancer
ALT	alanine aminotransferase
APaT	All Participants as Treated
aPTT	activated partial thromboplastin time
AST	aspartate aminotransferase
AUC	area under the curve
BCG	Bacillus Calmette–Guérin
BICR	blinded independent central review
BP	blood pressure
BRCA	breast cancer susceptibility gene
BTC	biliary tract cancer
BW	body weight
CI	confidence interval
CPK	creatine phosphokinase
CR	complete response
CD28	cluster of differentiation 28
C _{max}	maximum plasma concentration
CNS	central nervous system
CONSORT	Consolidated Standards of Reporting Trials
CRC	colorectal cancer
CrCl	creatinine clearance
CRF	Case Report Form
CRU	clinical research unit
CT	computed tomography
CTCAE	Common Terminology Criteria for Adverse Events
CTFG	Clinical Trial Facilitation Group
CTLA-4	cytotoxic T-lymphocyte-associated protein 4
CVA	cerebrovascular accident
CYP	cytochrome P450
DCR	disease control rate
DDI	drug-drug interaction
DILI	drug-induced liver injury
DLTs	dose-limiting toxicities
dMMR	mismatch repair deficient
DNA	deoxyribonucleic acid
DOR	duration of response
ECG	electrocardiogram
ECHO	echocardiogram
ECI	event of clinical interest
ECOG	Eastern Cooperative Oncology Group
eCRF	electronic Case Report Form
EDC	electronic data collection
ELISA	enzyme-linked immunoassay
EMA	European Medicines Agency
EOC	Executive Oversight Committee

Abbreviation	Expanded Term
EORTC	European Organisation for the Research and Treatment of Cancer
EOT	end of treatment
EQ-5D-5L	European Quality of Life 5-dimension 5-level
FDAAA	Food and Drug Administration Amendments Act
FFPE	formalin-fixed, paraffin embedded
FGF	fibroblast growth factor
FGFR	fibroblast growth factor receptor
FLAIR	fluid-attenuated inversion recovery
FSH	follicle-stimulating hormone
FU	follow-up
GBM	glioblastoma
gBRCAm	germline breast cancer susceptibility gene mutation
GCP	Good Clinical Practice
GEJ	gastroesophageal junction
GFR	glomerular filtration rate
GI	gastrointestinal
HBsAg	Hepatitis B surface antigen
HCV	Hepatitis C virus
HIV	human immunodeficiency virus
HRQoL	health-related quality of life
HRT	hormone replacement therapy
IA	interim analysis
IB	Investigator Brochure
ICF	Informed Consent Form
ICH	International Council for Harmonisation of Technical Requirements for Pharmaceuticals for Human Use
iCPD	iRECIST confirmed progressive disease
iCR	iRECIST complete response
iCRO	imaging Contract Research Organization
IEC	Independent Ethics Committee
Ig	immunoglobulin
IgG4	immunoglobulin G4
IgV-type	Ig-variable-type
IHC	immunohistochemistry
IL-10	interleukin 10
IMP	Investigational Medicinal Product
IND	Investigational New Drug
INR	international normalized ratio
IRB	Institutional Review Board
iRECIST	modified RECIST 1.1 for immune-based therapeutics
IRT	interactive response technology
iSD	iRECIST stable disease
IUD	intrauterine device
iUPD	iRECIST unconfirmed progressive disease
IUS	intrauterine hormone-releasing system
IV	intravenous
IVD	in vitro diagnostic
LVEF	left ventricular ejection fraction
mAb	monoclonal antibody
MMR	mismatch repair
mRNA	messenger RNA
MRI	magnetic resonance imaging
MSI	microsatellite instability

Abbreviation	Expanded Term
MTD	maximum tolerated dose
MUGA	multigated acquisition scan
NCI	National Cancer Institute
NDA	New Drug Application
NIMP	Non-Investigational Medicinal Product
NOAEL	no-observed-adverse-effect level
NSAID	nonsteroidal anti-inflammatory drug
NSCLC	non-small cell lung cancer
NYHA	New York Heart Association
OR	objective response
ORR	objective response rate
OS	overall survival
P-gp	P-glycoprotein
PARP	poly (ADP-ribose) polymerase
PBPK	physiologically based PK
PD	progressive disease
PD-1	programmed cell death 1
PDGFR	platelet-derived growth factor receptor
PD-L1	programmed cell death ligand 1
PD-L2	programmed cell death ligand 2
PE	physical examination
PFS	progression-free survival
PK	pharmacokinetic
PKC θ	protein kinase C-theta
PR	partial response
PRES	posterior reversible encephalopathy syndrome
PRO	patient-reported outcome
PT	prothrombin time
PTT	partial thromboplastin time
q3w	once every 3 weeks
qd	once daily
QoL	quality of life
QLG	Quality of Life Group
QLQ	Quality of life Questionnaire
RANO	Response Assessment in Neuro-Oncology
RCC	renal cell carcinoma
RECIST	Response Evaluation Criteria in Solid Tumors
RNA	ribonucleic acid
RP2D	recommended Phase 2 dose
RPLS	reversible posterior leukoencephalopathy syndrome
RTKi	receptor tyrosine kinase inhibitor
RTOG	Radiation Therapy Oncology Group
SAC	Scientific Advisory Committee
SAE	serious adverse event
SAP	statistical analysis plan
SGOT	serum glutamic oxaloacetic transaminase
SGPT	serum glutamic pyruvic transaminase
SIM	site imaging manual
SmPC	Summary of Product Characteristics
SoA	schedule of activities
sSAP	Supplemental Statistical Analysis Plan
SUSAR	suspected unexpected serious adverse reaction

Abbreviation	Expanded Term
TAM	tumor-associated macrophage
T1DM	type 1 diabetes mellitus
TAM	tumor-associated macrophage
TGF β	transforming growth factor, beta 1
T _{lag}	lag time
T _{max}	time to maximum plasma concentration
TMB	tumor mutational burden
TMDD	target-mediated drug disposition
TNBC	triple-negative breast cancer
T-reg	regulatory T-cells
TTD	time to deterioration
UDS	urine drug screen
ULN	upper limit of normal
UPCR	urine protein-to-creatinine ratio
VEGF	vascular endothelial growth factor
VEGFR	vascular endothelial growth factor receptor
Vp4	portal vein invasion
WOCBP	woman/women of childbearing potential
w/v	weight/volume
ZAP70	zeta-chain-associated protein kinase

